**Please do not copy this page when submitting paper copies to the IRB office.**

# Carilion Clinic Institutional Review Board Application

## REGISTRATION WITH DEPARTMENT OF RESEARCH & DEVELOPMENT

Per Institutional Policy, all IRB submissions must include the Research & Development (R&D) Authorization letter stating R&D has given you permission to submit to the IRB. Do you have your R&D Letter?

Yes (If yes, you MUST attach your R&D letter to this submission.)

No (*If no, do not submit this IRB application until you have your R&D letter.* You may contact R&D at [contact] or go to <http://insidecarilion.org/hubs/office-sponsored-projects/rd-forms-0.>)

## FINANCIAL CONFLICT OF INTEREST DISCLOSURE

Per Institutional Policy, all research team members on a funded study must submit a study-specific Financial Disclosure form through the Carilion Organizational Integrity and Compliance Office. Please contact [[contact]](mailto:[contact]) immediately to do so.

\*Please note it is the PI's responsibility to ensure all members of the research team have disclosed any financial or other relationships to the funding source. Failure to do so may be considered serious noncompliance and result in study suspension or termination.

**7. Sponsor:**

- Will this research be sponsored by an institution/entity outside of Carilion?  Yes  No
- If yes, name the institution/entity: **National Institute of Nursing Research**

**8. Funding Source:** If this study is or will be funded, every research team member MUST submit a study-specific Financial Disclosure form through the Carilion Organizational Integrity and Compliance Office immediately. Please contact [[contact]](mailto:[contact]) to do so. The IRB application cannot be approved until it is determined that there is not conflict, or that the conflict has been disclosed and managed.

- Carilion RAP grant
- Federal/state agency (specify): **National Institute of Nursing Research**
- Other grant (specify):
- Industry/commercial (specify):
- Private, non-profit (specify):
- No funding; equipment, supplies, and/or services will be provided (specify company):
- No funding; no equipment, supplies, and/or services will be provided
- Other (specify):

9. Is this the official project of a VTC SOM medical student as required for graduation and has already undergone scientific review by VTC SOM?

- Yes  No

10. Anticipated Start Date: **2/2019**

11. Estimated Time Needed to Complete Study: **1.5 years**

**SECTION II: DRUG, DEVICE AND BIOLOGIC STUDIES ONLY**

**N/A**

12. What is the name(s) of the drug, device or biologic that will be used in this study:

13. Please attach documentation to confirm FDA approval of this drug, device or biologic. Check one below:

- Package Insert
- Printed Information from the FDA website confirming FDA approval
- Letter from FDA granting approval
- Not available; FDA has not approved

14. Does the research study involve an Investigational New Drug (IND) or Biologic? An IND number is required if a drug or biologic is used in a manner outside the labeling approved by the FDA.

- Yes  No

- If yes, please provide the IND number assigned by the FDA. If an IND number is not available please explain why an IND was not obtained. If you believe the drug is exempt from IND approval, please submit an IND Determination form that can be found on the IRB web site. Note: Investigators may be asked to have an IND determination application submitted to the FDA.

15. Does the research involve a device that is being used outside the labeling approved by the FDA?

- Yes  No

If yes:

- Please provide the Investigation Device Exemption (IDE) number provided by the FDA:
- Attach one of the following:
  - FDA letter granting an IDE
  - A letter from the sponsor or investigator/sponsor stating the study device is non-significant risk
  - A letter explaining why the investigation is exempt from IDE requirements

16. Does this study meet the definition of an Applicable Clinical Trial (ACT) that requires registration on ClinicalTrials.gov? Whether yes or no, please complete the ACT Checklist and submit page 1 with your IRB application.

Yes       No

### SECTION III: STUDY PROTOCOL

17. **Study Abstract:** Provide a brief, non-technical summary of the study, including study purpose and methods.

**In this study, we will test whether a remotely delivered episodic future thinking (EFT) intervention, combined with dietary and activity coaching, as well as self-monitoring, reduces delay discounting and improves weight loss, glycemic control, and other health outcomes in patients with poorly controlled type 2 diabetes. Specifically, the study is a randomized trial comparing the effects of EFT versus a control condition on delay discounting, medication adherence, diet, physical activity, body weight, and glycemic control. Outcome measures will be assessed both remotely (e.g., online) and in the laboratory.**

18. **Background:** Summarize background information about the research question(s.) Tell why the research is needed and include the relevance of this research to the contribution of this field of study. Also, provide references to relevant articles in the literature. (If you have more than 10 references, please submit the list of references as a separate attachment. Otherwise, please insert them here.)

**Successful management of type 2 diabetes (T2D) requires a complex repertoire of behaviors, including adherence to physician-recommended medication, dietary, and exercise regimens (1, 2). Most of these behaviors provide little to no short-term benefit and may rather be aversive (e.g., physical exertion and caloric restriction). However, treatment adherence provides critical health benefits in the future, allowing patients with T2D to halt or reverse disease progression and avoid T2D-related complications (e.g., renal disease or diabetic retinopathy). Thus, successful management of T2D requires one's present behavior to be guided by future outcomes. Unfortunately, accumulating evidence indicates that individuals with T2D and those at risk for this disease rapidly devalue the future (3, 4), a phenomenon known as delay discounting. Moreover, within diabetic and prediabetic populations, we and others have shown that high rates of delay discounting are associated with poor treatment adherence and clinical outcomes (3, 4, 5). These data indicate that rapidly devaluing the future likely prevents successful management of T2D through a mechanism in which the health benefits of treatment adherence are too delayed to motivate present behavior. Thus, we believe delay discounting serves as a therapeutic target in T2D, in which improving valuation of the future will improve treatment adherence and, in turn, improve health outcomes such as glycemic control and body weight.**

**Episodic future thinking (EFT) is a form of prospection that involves mental simulation of events that might occur in one's future (6). EFT to some extent is an innate human ability that guides decision-making (e.g., simulating the experience of an upcoming job interview or social event); however, populations who discount the future rapidly show deficits in this ability, considering the future infrequently and**

demonstrating low-quality EFT content (e.g., fewer contextual and sensory details). Thus, EFT interventions are designed to remediate this deficit and reduce bias toward immediate gratification by guiding individuals to both generate high-quality EFT content and prompting them to engage in EFT frequently. Prior laboratory-based research by the investigative team and others has shown that EFT reduces both delay discounting and a wide range of maladaptive health behaviors and outcomes, including overeating (7), food purchasing (8), and weight control in overweight and obese populations (9).

These therapeutic effects suggest that EFT may be used to reduce the bias for immediate gratification observed in T2D, and thus improve valuation of the long-term outcomes associated with treatment adherence. However, little research has examined the efficacy of EFT in the real world. This gap in knowledge presents a challenge to our understanding of the etiology and treatment of this disease. Therefore, our goal is to leverage prior extensive research to engage our behavioral target, delay discounting, to develop a clinical intervention for T2D. In pursuit of our goal, our objective in this study is to develop a practical, remotely delivered EFT intervention to improve delay discounting and treatment adherence in T2D and, in so doing, improve management of T2D.

**Specific Aim 1** will examine the effects of a 4-month, remotely delivered EFT intervention on delay discounting, medication adherence, diet, physical activity, body weight, and glycemic control in patients with poorly controlled T2D. All participants will receive access to a standard behavioral treatment (BT), including lifestyle coaching, dietary and activity education, and daily self-monitoring. Participants assigned to an EFT+BT group will also be asked to generate vivid, episodic events and be sent text-based prompts daily to engage in EFT in the natural environment with the assistance of a study website. Participants assigned to a BT alone group will not receive EFT, but will be asked to access the study website and answer questions about their experience with the same frequency as the EFT group in order to control for use of the technology, effort, attention, and experimenter contact. We will assess outcome measures both during and immediately after the intervention, as well as at a 6-month follow-up session (approximately 2 months following the end of the intervention). This will allow us to estimate both short- and long-term effects changes in behavior, weight, and glycemic control

**Specific Aim 2** will examine the acceptability of the remote EFT intervention. In order for an intervention to be effective in clinical settings, it should be easy to use and its helpfulness should be apparent. Thus, during the trial and follow-up, participants will rate all aspects of the interventions along several dimensions, including helpfulness and ease of use. High intervention ratings would suggest that EFT may be implemented with high treatment fidelity in clinical settings and is more likely to be disseminated among treatment providers and adopted by patients.

20. **Study Design:** Give a description of the research design including use of placebo, randomization and an explanation of what is experimental. Include type of study: descriptive, retrospective, cross-sectional, longitudinal, prospective observational, pilot, experimental (controlled or non-controlled) or pilot.

**This is a randomized control trial in which we randomly and experimentally assign participants to either an EFT or control group and examine the impact of that assignment on study outcomes. All participants will also receive access to a lifestyle intervention, case management, and self-monitoring.**
21. **Study Population:** Describe the subject population, including age, gender, ethnic characteristics and health status. State the inclusion/exclusion criteria along with how this was determined, and by whom. Please state whether pregnant women, children, or other vulnerable groups will be included or excluded. Provide rationale for using or excluding special populations. State the number of subjects or subject records necessary to complete the research.

**We will enroll up to 150 patients with type 2 diabetes (N = 54, plus addition to account for screen failure following an initial screening session, possible dropout, etc.). Recruitment will focus on patients who do not adequately control their blood**

sugar because this is the subpopulation of diabetes patients in greatest need of intervention. .

**Inclusion Criteria:**

- age 18 or over
- type 2 diabetes diagnosis
- prescribed or recommended oral glucose-lowering medication for type 2 diabetes
- HbA1c level of ~8% or greater
- body mass index of 25 or greater

**Exclusion criteria**

- current insulin therapy for type 2 diabetes
- history of gestational diabetes
- pregnant or lactating (if female), or plans to become pregnant in the next 6 months
- not ambulatory
- intellectual impairment that would impact treatment adherence or the ability to provide informed consent
- medical conditions that affect behavioral or medical adherence: Participants should not have a medical condition that would limit participation such as individuals with medical conditions that may affect their ability to use the computer for a prolonged period of time or follow study protocol will also be excluded, current diagnosis with an eating disorder or an unmanaged psychiatric disorder
- abnormal glucose related to medications (e.g. atypical antipsychotic medications or glucocorticoids)
- prior participation in similar studies: Individuals who have recently participated in a laboratory study using similar methods may also be excluded.

22. **Methodology:** List all activities or procedures that will be performed (pre-treatment tests and medications, tests and medications used during therapy, diagnostic tests, x-rays, lab tests, questionnaires and other forms, interviews, chart reviews etc.) Describe how, when and where research activities will be administered and analyzed. **Distinguish any standard processes from those that are research.** Please describe activities/procedures in a step-by-step chronological order. State the length of time subjects will be in the study and the expected amount of time required for each study visit or activity.

Individuals who are likely eligible based on the online screening questionnaire (see Appendix A: pre-screening questionnaire) will be invited to attend a lab session. After providing informed consent at the lab session, participants' blood HbA1c, height, and weight will be measured, as well as provide demographic, health, and medication information, and complete delay discounting and food purchase tasks. Participants who are verified to be eligible from lab-based and online screening, will continue with the remainder of the study and will be randomly assigned to either an EFT+BT group or BT control group. Those who are deemed ineligible at this stage (e.g., due to low HbA1C) will be provided with prorated compensation and informed that they do not qualify. If participants are determined to be eligible, they will be given a detailed orientation of what will be expected of them during the study, including tasks they need to complete, recording food consumption and activity levels, and frequency of visits to our lab.

Eligible participants will then initiate further study procedures, consisting of: 1) laboratory assessment sessions, 2) physical activity assessments, 3) case management meetings, 4) daily self-monitoring of diet, weight, and activity, and 5) EFT or control engagement. The intervention will last approximately from Weeks 0-16, with an additional follow-up assessment at Week 24).

**-Laboratory Assessment Sessions (Weeks 0, 8, 16, and 24)**

At assessment sessions, we will collect measures of blood HbA1c, blood pressure, height, and weight. Participants will also complete delay discounting tasks, food purchase tasks, and complete other study questionnaires (e.g., demographics).

**-Physical Activity Assessments (Weeks 0, 8, and 16).**

Participants will be provided with an Actigraph accelerometer for use during the study and instructed how to properly wear it. At each assessment (Weeks 0, 6, and 16), participants will be asked to wear the accelerometer for a continuous 7-day period. Although these assessments are scheduled to take place during Weeks 0, 8, and 16, the 7-day period may occur during adjacent weeks, in whole or in part, to facilitate scheduling. After the 7-day period of Actigraph wear, participants will be asked to return the device until the next assessment or at the end of the study.

**-24-hour Dietary Recalls (Weeks 0, 8, and 16)**

On three days during approximately the same period that participants wear the Actigraph, participants will be asked to complete 24-hour diet recalls using the Automated Self-Administered 24-hour Dietary Assessment Tool (ASA-24).

Participants may complete these recalls online.

**-Case management meetings (Weeks 0-16).**

All participants in both groups will attend weekly (during approximate Weeks 1-8) and bi-monthly (during approximate Weeks 8-16) meetings with a case manager. These meetings will occur over the phone, unless the participant prefers to visit the laboratory. At these meetings, participants will be provided general information on healthy diet, physical activity and medication adherence. Participants will also be provided instruction regarding a number of different healthy habits for patients with type 2 diabetes, including: 1) The Traffic Light Diet, which utilizes RED, YELLOW, and GREEN labels for food to guide participants toward the goal of consuming low energy dense, low glycemic, high nutrient dense foods; 2) the Traffic Light Activity Program, which also utilizes RED, YELLOW and GREEN labels for different levels of caloric expenditure, 3) a variety of behavioral techniques, including meal planning and 4) use of EFT or the control condition. Participants will be provided with educational reading materials for each of these topics, be asked to read these materials in between meetings, and be asked to complete quizzes to assess mastery (see Appendix B: Healthy Habits Manual + Quizzes). These materials will most often be provided in Qualtrics software, but may also be provided in paper form. These meetings will also review information about weight loss and maintenance, engage in problem solving for participants who are struggling with behavior change, behavior change techniques, and diet and activity self-monitoring, and other topics relevant for weight and diet management. The case manager will also provide instruction for using either EFT for behavior change for the EFT+BT group, as well as how to access the study website for the BT control group.

At the end of the intervention period (approximately Week 16), case management meetings will be discontinued. However, participants will retain access to educational materials in Qualtrics through Week 24.

**-EFT/Control engagement (Weeks 3-16).**

Beginning in Week 2, participants will be randomly assigned to either the EFT+BT or BT control groups. Participants in the EFT+BT group will be asked to generate episodic cues similar to the tasks used in our previous studies on EFT's effect (Daniel et al., 2013). Participants will list and describe events for different time periods. The episodic component of the thinking task will occur while the participants are asked to describe what they are imagining about each event (e.g., vacations, weddings, parties, health goals, etc.). EFT participants will list positive future events they are looking forward to and list events that could happen at different general future time points (e.g., 1 month, 2-6 months, 7-12 months). Participants will also create text-based cues for each event, which will consist of descriptions of the future event (e.g., "In about 6 months, I am attending my sister's wedding in Montana. I am enjoying the crisp air and getting to see my family again."). In contrast, the BT control group will not generate these events.

For the remainder of the intervention, participants in both groups will be sent text-based prompts via cell phone to access the study website (built in Qualtrics survey software). Once accessed, the study website will guide EFT+BT participants to engage in EFT by presenting cues. Brief questions may also be presented asking participants to describe their study experience (e.g., "Have you encountered any diet or activity challenges today?"). Participants in the BT control group will only be prompted to access the study website to answer these questions.

Experimenters will train participants in both groups on how to access the study website from their cell phone or alternative internet accessible device (e.g. laptop, tablet, desktop computer), as well as how to pay attention to and think about the cues, and how to adhere to the study's expectations for utilizing the cues (EFT+BT group only). Participants may be prompted several times a day to access the website and, for the EFT+BT group, instructed to use their cues any time that need to, especially around eating episodes.

At the end of the intervention period (approximately Week 16), participants will retain access to educational and other materials in Qualtrics through Week 24. However, participants will not be provided with prompts to access these materials during this period and will not be required to use the website.

#### **-Diet, activity, and weight self-monitoring (Weeks 1-16).**

Participants will be taught how to record food, drink, exercise, and at home weight measurements in MyFitnessPal (see Appendix C: Study Websites). MyFitnessPal is a smartphone and web based app that tracks diet and exercise and can record the number of calories, macro and micronutrients consumed. Participants will be asked to use MyFitnessPal for self-monitoring throughout the study, recording the amount and types of food they eat and activity they engage in, as well as their weights. User accounts will be created for participants and will not include any identifying information.

At the end of the intervention period (approximately Week 16), participants may retain access to MyFitnessPal through Week 24 to continue self-monitoring of diet, exercise, and weight. However, participants will not be required to use this software during this period.

## **References**

1. Sze, Yan Yan, Tinuke Oluyomi Daniel, Colleen K. Kilanowski, R. Lorraine Collins, and Leonard H. Epstein. "Web-based and mobile delivery of an episodic future thinking intervention for overweight and obese families: a feasibility study." *JMIR mHealth and uHealth* 3, no. 4 (2015).

23. **Data Collection:** Describe below the data collection methods and how data be compiled for assessment. Attach a copy of your data collection tool or spreadsheet listing exactly what data is to be gathered during this research study. If all data is retrospective, please state date range from which data will be collected and note that data must be in existence at time of submission of this application.

**All protected health information will be stored on a password-protected spreadsheet on RedCap provided through Carilion Clinic and linked only to subjects through a subject ID number.**

**Additional de-identified study data will be collected and stored using Qualtrics survey software. These data will be linked to the participants through their subject ID (in RedCap).**

**These de-identified study data include the following measures, which may also be found in the attached appendix (see Appendix D: Study Measures).**

--Demographic variables and health behavior data. Race/ethnicity, household income, and educational level will be assessed at baseline using a survey-based questionnaire. Participants will also be asked about their health and related behaviors (e.g., mental health, medical history, financial behaviors, and food consumption.)

--Eating Disorder Diagnostic Scale. This 22-item self-report scale screens for the presence and severity of symptoms associated with anorexia nervosa, bulimia nervosa, and binge-eating disorder assess. Participants who provide scores consistent with an eating disorder will be provided with referrals to the National Eating Disorder's Helpline [contact]), local resources, and/or will be counseled to speak with their personal physician.

--Weight, height, BMI. Participants' weight will be assessed using a digital scale. Height measurements will also be collected. On the basis of height and weight, BMI is calculated according to the following formula: (BMI=kg/m^2).

--Blood HbA1c. Hemoglobin A1c (HbA1c) will be measured using the Alere Affinion system.

--Blood Pressure. Blood pressure will be measured in triplicate using an automated blood pressure device by trained personnel. The latter two readings will be averaged.

--Dietary restraint. Participants will complete the three-item "Dietary Restraint" portion of the Three Factor Eating Questionnaire (TFEQ) (Stunkard & Messick, 1985), a validated instrument to detect dietary restraint (Allison, Kalinsky, & Gorman, 1992).

--Treatment effectiveness and ease of use. Participants will rate multiple components of the intervention (e.g., EFT prompts, self-monitoring) on dimensions of perceived effectiveness and ease of use using 5-point Likert scales.

--**Delay discounting.** Participants will complete hypothetical delay discounting tasks for different commodities (e.g. delayed money, weight loss). These tasks assess preference between a small, immediately available reward (e.g., \$50 now) and a larger, delayed reward (e.g., \$100 in 6 months) across multiple trials and delays (e.g., 1 day through 25 years). This task reveals how the subjective value of a reward decreases with increases delay. The steepness of the discounting curve, estimated by the parameter  $k$ , provides a measure of delay discounting.

--**Medication adherence.** Adherence to oral glucose-lowering medication (e.g., Metformin) will be assessed by both a self-report questionnaire and by direct observation (pill count). In the self-report questionnaire, participants will complete a questionnaire in which they report how often they have taken their prescribed medication in the recent past. In the direct observation assessment, participants will be asked to bring their prescription bottles to both baseline and follow-up visits. Remaining pills will be counted and medication adherence will be calculated as:  $(\text{quantity dispensed} - \text{remaining}) / (\text{quantity prescribed per day} * \text{days since last refill}) * 100$ , yielding a measure of percent adherence.

--**Relative reinforcing efficacy of food.** Hypothetical food purchase tasks will assess the relative reinforcing efficacy of a range of foods. In this task, participants report the hypothetical quantity of foods they would purchase to consume across a range of prices (e.g., \$0.01 - \$30 per serving).

--**Dietary intake.** Diet will be assessed by self-reporting using the Automated Self-Administered 24-hour Dietary Assessment Tool (ASA-24)

--**Corsi block tapping task.** In this test of working memory, blocks are presented on a computer screen, which light up one at a time in random order and in sequences of increasing length. After each presentation, participants attempt to reproduce the patterns shown.

--**Physical activity.** Physical activity will be measured using an Actigraph accelerometer. Participants will complete three Actigraph assessments during the study, with each assessment lasting 7 days. Total activity counts and activity in the moderate to vigorous (MVPA) and vigorous (VPA) ranges, among other measures, will be estimated.

--**Patient Health Questionnaire.** This questionnaire assesses frequency of depressive symptoms.

24. **Statistical Analysis:** State how qualitative and/or quantitative data will be analyzed. This must include a statement from a statistician that there is sufficient power to determine the primary study outcome or objective. Other outcomes may be listed as secondary and descriptive. If this is a proof of concept or feasibility study that includes limited efficacy testing, there must be a statistician statement that the appropriate design is in place to determine whether an intervention should be recommended for broader efficacy testing. If a study is meant to be solely descriptive, then results apply only to the sample being studied and conclusions cannot be drawn about the larger population; therefore, the primary outcome or objective must be limited in scope.

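### The pill count asks only for prescription bottles, so pills kept in an organizer are scored as taken and inflate percent adherence

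*Combined protocol and SAP*

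**What the plan says.** Section III, item 23 (Data Collection), under Medication adherence, defines two measures: a self-report questionnaire and a pill count, which the plan describes as direct observation. For the pill count, "participants will be asked to bring their prescription bottles to both baseline and follow-up visits. Remaining pills will be counted". The score is the number dispensed minus the number remaining, divided by the product of the "quantity prescribed per day" and the "days since last refill", times 100, "yielding a measure of percent adherence".

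The text names no container other than prescription bottles. It sets no upper limit and no rule for implausible values, and it does not link the count to the questionnaire. Item 23 refers to Appendix D for the study measures; that appendix is not among the documents supplied.

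Medication adherence is part of Specific Aim 1 (item 18), is a secondary outcome in item 19, and is analysed by repeated measures ANOVA in item 24. Under Case management meetings in item 22, which apply to both arms, "participants will be provided general information on healthy diet, physical activity and medication adherence".

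**The concern.** The formula infers pills taken from pills not found. It is right only if every untaken pill is in front of the person counting. Some patients move tablets from the bottle into a weekly organizer or a travel container. If a participant does so and brings only the bottles, as asked, the untaken tablets in the other container are scored as taken.

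The pill count is the only adherence measure in the plan that does not rely on self-report. The size of the error depends on how many pills are displaced and on how long ago the refill was. The plan fixes neither, so the error can differ between visits for the same person and enter an analysis of change as if it were a change in behaviour. It does not depend on pills carried over from an earlier fill: it can occur in a first fill with nothing left over.

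**Working it through.** **The plan's own figure.** The plan gives no worked figure for the pill count. Its only computed figure is the sample size in item 24. For the group-by-time interaction with two measurements, f = 0.25 and correlation 0.50, the noncentrality is 0.25² × 54 × 2 / (1 − 0.50) = 13.5 on 1 and 52 degrees of freedom. Power is 0.9501, so N = 54 reproduces. Nothing below changes it.

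**Inputs.** The formula and the request for bottles come from item 23. The following are assumptions, because the documents give no values: D = 60 pills dispensed, q = 2 per day, true adherence 70%, and M = 14 pills (7 days of supply) in an organizer. Days since refill, d, is varied.

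**General result.** Let T be the pills actually taken. The bottles hold D − T − M, so

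score = 100 × [D − (D − T − M)] / (q × d) = 100 × T/(q × d) + 100 × (M/q)/d.

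The first term is true adherence. The second is the inflation: days of supply displaced, divided by days since refill, times 100. The score cannot exceed 100 × D/(q × d), which is reached when the bottles are empty.

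**Numbers, 14 pills displaced** (inflation 700/d):

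| d | Taken | In bottle | Score as written | Organizer also counted |
|---|---|---|---|---|
| 30 | 42 | 4 | 56/60 = 93.3% | (60 − 18)/60 = 70% |
| 20 | 28 | 18 | 42/40 = 105% | (60 − 32)/40 = 70% |
| 15 | 21 | 25 | 35/30 = 116.7% | (60 − 39)/30 = 70% |

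**Numbers, 7 pills displaced** (a half-used organizer, inflation 350/d): 81.7% at day 30, 87.5% at day 20 and 93.3% at day 15.

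**Longer interval.** At day 60, with a fill that lasts that long, 14 pills add 700/60 = 11.7 points and 7 pills add 5.8.

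**When the score passes 100%.** This needs 70 + 700/d > 100, so d < 23.3 days with 14 pills displaced, or d < 11.7 days with 7. With 60 pills and d = 30 the ceiling is exactly 100 × 60/(2 × 30) = 100%.

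**Spurious change.** If the same person has 14 pills in the organizer at both visits, counted at d = 30 and then d = 20, the score moves from 93.3% to 105%. That is 11.7 points with no change in behaviour. If d and the displaced quantity are the same at both visits, the inflation cancels from the change.

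**Effect of a cap alone.** At day 15 a cap turns 116.7% into 100%, still 30 points above the true 70%. At day 30 it does nothing, since 93.3% is already below 100%.

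**The case against.** Several arguments limit this point, and most of them stand.

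- **Frequency is unknown.** Organizer use, pill numbers and refill timing are all assumed. This stands: the working shows the size per affected participant, not the effect on a group mean.
- **The text does not say that only bottles count.** The sentence on counting is not itself restricted to bottles, and Appendix D may hold fuller instructions. This stands as a caveat. However, participants who do what the visible text asks would leave an organizer at home, and nothing supplied corrects for that.
- **Pills in a second bottle.** A reader might infer that these are also missed. The documents do not support that, because the request is for bottles in the plural.
- **Lost or discarded pills.** A reader might count these as a fault of this plan. They are a limit of any pill count, and no instruction to the participant recovers them.
- **Bias between arms.** A reader might infer that adherence coaching raises organizer use after baseline and favours one arm. Item 22 gives the same meetings to both arms, describes only general adherence information and does not mention organizers. Nothing suggests different uptake.
- **Direction of error.** It would be too strong to say that the formula always overstates adherence. If 14 pills from an earlier fill are left in the same bottle, the same 70% adherent person at day 14 has taken 19.6 pills and scores (19.6 − 14)/28 = 20%.
- **Materiality.** Adherence is a secondary outcome with a parallel questionnaire. This stands, although no rule uses the questionnaire to correct the count.

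**Conclusion.** The point holds as a minor, inexpensive improvement to a stated measurement rule. Followed as written, item 23 scores pills held in an organizer or other non-prescription container as taken and adds 100 × (days of supply displaced)/(days since refill) points. In the assumed example that is 23 points at day 30 and 35 at day 20 with a full week displaced, and half of that with half a week. The main consequences are extra noise in the arm comparison and possibly a false within-person change.

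It would be wrong to conclude that scores above 100% are the typical result. For a 70% adherent participant with a full week displaced, they need a count less than about 23 days after the refill; later counts are inflated but stay under 100%. The primary outcomes and N = 54 are not affected. The conclusion rests on the assumed inputs above and on Appendix D not already giving a broader counting instruction.

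**What to change.** Replace the request for bottles in item 23 with wording such as: *Participants will bring all remaining glucose-lowering pills, wherever stored (prescription bottles, organizers, other containers), and all will be counted as remaining.* Use the same wording in the visit reminder. If Appendix D already says this, bring item 23 into line with it.

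Add that values above 100% will be flagged and their number reported by arm as a data-quality check, since such a value suggests that a count or a refill date is wrong. A cap at 100% is optional: it trims one direction of error and hides that signal without repairing the measure.

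The cost is a slightly longer reminder and a few more pills to count at the visit. Lost or discarded pills will still be scored as taken, and the report should say so.
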